10.2.4.1.2. Summaries

For the SAF and PAS, the following summaries will be produced by MedDRA term (if 10 or fewer participants appear in a table, a listing may be appropriate):

- TEAEs by SOC and PT
- TEAEs by SOC, PT, and CTCAE grade category
- Grade 3 or higher TEAEs by SOC and PT
- Grade 3 or higher TEAEs by PT in decreasing order of frequency
- TEAEs by SOC, PT, and highest intensity
- TEAEs by SOC, PT, and maximum severity
- TEAEs by PT in decreasing order of frequency
- Serious TEAEs by SOC and PT
- Serious TEAEs by SOC, PT, and CTCAE grade category

- Grade 3 or higher serious TEAEs by SOC and PT
- Serious TEAEs by PT in decreasing order of frequency
- Treatment-related serious TEAEs by SOC and PT
- TEAEs with a fatal outcome by SOC and PT
- Treatment-emergent AESIs by SOC and PT
- Treatment-emergent AESIs by SOC, PT, and CTCAE grade category
- Grade 3 or higher treatment-emergent AESIs by SOC and PT
- TEAEs leading to tafasitamab infusion interruption by SOC and PT
- TEAEs leading to tafasitamab infusion interruption by SOC, PT, and CTCAE grade category
- TEAEs leading to skipped tafasitamab infusion by SOC and PT
- TEAEs leading to skipped tafasitamab infusion by SOC, PT, and CTCAE grade category
- TEAEs leading to skipped LEN dose by SOC and PT
- TEAEs leading to skipped LEN dose by SOC, PT, and CTCAE grade category
- TEAEs leading to LEN dose reduction by SOC and PT
- TEAEs leading to LEN dose reduction by SOC, PT, and CTCAE grade category
- TEAEs leading to discontinuation of tafasitamab by SOC and PT
- TEAEs leading to discontinuation of LEN by SOC and PT
- Treatment-related TEAEs by SOC and PT
- Treatment-related TEAEs by SOC, PT, and CTCAE grade category
- Treatment-related TEAEs by PT in decreasing order of frequency
- Tafasitamab-related TEAEs by PT in decreasing order of frequency
- LEN-related TEAEs by PT in decreasing order of frequency
- Grade 3 or higher treatment-related TEAEs by SOC and PT
- Tafasitamab-related TEAEs by SOC and PT
- Tafasitamab-related TEAEs by SOC, PT, and CTCAE grade category
- Grade 3 or higher tafasitamab-related TEAEs by SOC and PT
- LEN-related TEAEs by SOC and PT
- LEN-related TEAEs by SOC, PT, and CTCAE grade category
- Grade 3 or higher LEN-related TEAEs by SOC and PT
- Infusion-related TEAEs by SOC and PT

- Infusion-related TEAEs by SOC, PT, and CTCAE grade category
- Grade 3 or higher infusion-related TEAEs by SOC and PT
- TEAEs by SOC, PT, and outcome
- TEAEs by SOC, PT, and action taken with tafasitamab
- TEAEs by SOC, PT, and action taken with LEN

Deaths in the SAF and PAS will be summarized if they occur pretreatment, on treatment, or post-treatment and if due to disease progression or an AE. An overall summary of deaths will be generated for the SAF and PAS. The number (%) of participants with events will be presented.

Figures summarizing the TEAEs (broken down by grade) will be presented for the following:

- All TEAEs by PT
- Hematologic TEAEs by PT
- Nonhematologic TEAEs by PT

Time to onset since Cycle 1 Day 1 of the PTs neutropenia and febrile neutropenia will be summarized.

Time to onset since the first dose of tafasitamab 24 or 30 mg/kg of the PTs neutropenia and febrile neutropenia will be summarized.

10.2.4.2. Summaries of Treatment-Emergent Adverse Events and Deaths for the Enrolled Population Set

10.2.4.2.1. Summaries

For the ENR, an overall summary of AEs by treatment group will include the same information described in Section 10.2.4.1.2.

For the ENR, the following summary tables showing the number (%) of participants will be provided by tafasitamab dose group and overall:

- TEAEs by SOC and PT
- TEAEs by SOC, PT, and CTCAE grade category
- Grade 3 or higher TEAEs by SOC and PT
- Serious TEAEs by SOC and PT
- Serious TEAEs by SOC, PT, and CTCAE grade category
- Grade 3 or higher serious TEAEs by SOC and PT
- TEAEs by SOC, PT, and initial intensity
- Treatment-emergent AESIs by SOC and PT
- Treatment-emergent AESIs by SOC, PT, and CTCAE grade category
- Grade 3 or higher treatment-emergent AESIs by SOC and PT

Deaths in the ENR will be summarized if they occur pretreatment, on treatment or post-treatment and if due to disease progression or an AE. An overall summary of deaths will be generated for the ENR. The number (%) of participants with events will be presented.

10.2.5. Adverse Event and Death Listings

All AEs/TEAEs will be listed by cohort and treatment group and sorted by participant identification number along with the start date (day) and end date (day), duration, if serious, if an AESI, if related to tafasitamab/LEN, toxicity grade (highest), action taken with tafasitamab/LEN, other actions taken, tafasitamab start/end dates, LEN start/end dates, outcome, earliest date participant received prohibited concomitant medication (if applicable), and a flag to evaluate whether predefined safety event criteria are met. Listings will be generated for the ENR, with inclusion in the SAF and PAS noted, for the following:

- All AEs recorded throughout the study to show all information captured in the "Adverse Event" eCRF. The listing will include a flag to evaluate if the AE meets the predefined safety events criteria.
- All infusion-related AEs recorded throughout the study to show all information captured in the "Adverse Event" eCRF.
- All SAEs recorded throughout the study to show all information captured in the "Adverse Event" eCRF, including criteria for SAE met.
- All AESIs recorded throughout the study to show all information captured in the "Adverse Event" eCRF, including criteria for AESI met.
- All AEs with an onset date after the start date of prohibited concomitant medication.

All deaths, with an indicator if death occurred pretreatment, on treatment, or post-treatment, will be listed by cohort and treatment group and sorted by participant identification number along with the date of death (day) and cause of death, tafasitamab start/end dates, LEN start/end dates, and if applicable, earliest date participant received prohibited concomitant medication. The listing will be generated for the ENR, with inclusion in the SAF and PAS noted, and will include all assessments/events and a flag for those that are pre- and post-treatment assessments/events.

10.3. Clinical Laboratory Tests

10.3.1. Laboratory Variables

Laboratory assessments will be performed by local laboratories for the following categories:

- Hematology
- Chemistry
- Coagulation
- Liver biochemistry
- Serology/virology
- Urinalysis
- Pregnancy

10.3.2. Laboratory Value Definitions

Baseline will be determined according to Section 4.1.4. If there are multiple values that meet the criteria for baseline, scheduled assessments will take precedence over unscheduled.

Laboratory test values will be assessed for severity based on the numerical component of NCI CTCAE v5.

For laboratory tests for which grades of severity are not defined by NCI CTCAE, results will be graded by the low/high or normal/abnormal classifications based on laboratory normal ranges.

10.3.3. Laboratory Value Summaries

Results will be presented for the SAF.

All test results and associated normal ranges will be reported in SI units. Any laboratory test results and associated normal ranges from local laboratories will be converted to SI units.

If there are multiple nonmissing laboratory values for a participant's particular test at a scheduled visit, scheduled assessments will take precedence over unscheduled.

Numeric laboratory values will be summarized descriptively in SI units, and non-numeric test values will be tabulated when necessary.

Severity grades will be assigned to laboratory test values based on the numerical component of NCI CTCAE v5. Shift tables will be presented showing change in CTCAE grade from baseline to worst grade postbaseline. Separate summaries for abnormally high and abnormally low laboratory values will be provided when the laboratory parameter has both high and low grading criteria. The denominator for the percentage calculation will be the number of participants in the baseline category. The number of participants who had worsening of laboratory abnormalities will be summarized by maximum severity. Data on absolute neutrophil count, platelets, and hemoglobin will be visually summarized using box plots.

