### 3.5.3 Overall Benefit Risk Conclusion

The estimand is described by the following attributes:

**Population:** All R/R DLBCL patients who receive at least [REDACTED]

**Endpoint:** Incidence and severity of TEAEs.

TEAEs are defined as all AEs which start or worsen after the first dose of study treatment until 90 days after the last dose of the study treatment.

**Treatment condition:** Treatment consisting of tafasitamab and LEN combination will be administered until disease progression, unacceptable toxicity, or discontinuation for any other reason, whichever comes first. LEN can be given for up to 12 cycles in total, after which patients can continue with tafasitamab as monotherapy until progression or unacceptable toxicity.

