### 10.3.3 Safety Analyses (Primary Endpoint)

The primary objective of this study is to evaluate the safety and tolerability of [REDACTED] tafasitamab i.v. [REDACTED] combined with LEN in patients with R/R DLBCL.

As this is a Phase 1b/2 study, no formal hypothesis testing will be performed.

To assess safety and tolerability, the incidence and severity of hematological and non-hematological AEs including clinically significant laboratory abnormalities will be determined. AEs will be categorized with regards to seriousness, intensity, toxicity, study treatment relationship, outcome and action taken. AE reports will be graded according to National Cancer Institute (NCI) Common Terminology Criteria for AEs (CTCAE), version 5.0.

All Safety Analyses will be presented by [REDACTED].

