### ***10.3.7.2 Clinical Laboratory Evaluation***

The analysis of local laboratory parameters for each treatment arm will be presented, separated into blood parameters (e.g., hematology, serum chemistry, coagulation, serology for hepatitis B and C) urine parameters (e.g., urinalysis) and serum pregnancy test.

All data collected in the course of the study will be listed.

The following analyses will be performed, where appropriate, for measurements of hematology and blood chemistry tests:

- Standard descriptive statistics for values measured at baseline and post-baseline visits including changes from baseline
- For selected laboratory parameter, shifts in assessments from baseline to worst-post baseline value
- Number (and percentage) of patients with clinically significant changes for selected tests

Each abnormal value measured in the local laboratory will be flagged to show whether it is a value below or above the reference range for the given local laboratory. For the assessment of laboratory variables, the investigator will need to judge their clinical significance.

The assessment of the clinical significance of central laboratory variables will be tabulated by time point for each clinical laboratory value using frequency tabulations.

Clinical laboratory values with available NCI-CTCAE grades may be presented with additional frequency and shift tables based on these grades.

Laboratory values that are outside the reference range will also be flagged in the data listings, along with the corresponding reference ranges.

The analyses will be performed on PAS and SAF. Further details will be specified in the SAP.

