5.3.5. Safety Analysis Set

The SAF will include all participants who received at least 1 dose of study drug (tafasitamab or LEN) and had at least 1 postbaseline safety assessment. A valid safety assessment includes death. Treatment groups for this set will be determined according to the actual treatment the participant received regardless of assigned study treatment.

All safety analyses will be conducted using the SAF.

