10.2.4.1.1. General Considerations

The primary safety analysis will be performed for the PAS, and a supplemental safety analysis will be performed for the SAF. The number (%) of participants who had any TEAE will be provided along with the TEAE incidence. Treatment-emergent AEs that occur after the start date of a prohibited concomitant medication will be excluded from the primary and supplemental safety analyses. No TEAE data will be collected after withdrawal of consent.

Treatment-emergent AEs will be classified into the following categories: seriousness, causality (suspected relationship to study treatment), toxicity (determined according to CTCAE v5), intensity, outcome, and action taken.

Specifically, all summaries of treatment-related TEAEs (causality) will be divided into the following 4 sections: related to any component of study treatment, related to tafasitamab only, related to LEN only, and related to both tafasitamab and LEN.

All summaries of TEAEs leading to treatment discontinuation will be divided into the following sections: discontinuation of tafasitamab, discontinuation of LEN, discontinuation of both tafasitamab and LEN.

The incidence of TEAEs will be summarized in incidence tables. If a participant experiences more than 1 occurrence of the same TEAE, the occurrence with the greatest intensity/toxicity, worst outcome, worst action taken, or the closest association with the study treatment will be counted in the summary tables.

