3.2.20.1.x	Summary of Treatment-Emergent Adverse Events Leading to Discontinuation of Tafasitamab by MedDRA System Organ Class and Preferred Term	SAF (.1), PAS (.2)	X
3.2.20.2.x	Summary of Treatment-Emergent Adverse Events Leading to Discontinuation of Lenalidomide by MedDRA System Organ Class and Preferred Term	SAF (.1), PAS (.2)	X
3.2.24.1.x	Summary of Deaths	SAF (.1), PAS (.2), ENR (.3)	X
3.2.24.2	Summary of Deaths Caused by COVID-19	ENR	X
3.2.25.x	Summary of Treatment-Emergent Adverse Events by MedDRA System Organ Class, Preferred Term, and Highest Intensity	SAF (.1), PAS (.2), ENR (.3)	X
3.2.26.x	Summary of Infusion-Related Treatment-Emergent Adverse Events by MedDRA System Organ Class and Preferred Term	SAF (.1), PAS (.2)	X
3.2.27.x	Summary of Infusion-Related Treatment-Emergent Adverse Events by MedDRA System Organ Class, Preferred Term, and CTCAE Grade Category	SAF (.1), PAS (.2)	X

Table No.	Title	Population	Standard
3.2.28.x	Summary of Grade 3 or Higher Infusion-Related Treatment-Emergent Adverse Events by MedDRA System Organ Class and Preferred Term	SAF (.1), PAS (.2)	X
3.2.29.x	Summary of Treatment-Emergent Adverse Events of Special Interest by MedDRA System Organ Class and Preferred Term	SAF (.1), PAS (.2), ENR (.3)	X
3.2.30.x	Summary of Treatment-Emergent Adverse Events of Special Interest by MedDRA System Organ Class, Preferred Term, and CTCAE Grade Category	SAF (.1), PAS (.2), ENR (.3)	X
3.2.31.x	Summary of Grade 3 or Higher Treatment-Emergent Adverse Events of Special Interest by MedDRA System Organ Class and Preferred Term	SAF (.1), PAS (.2), ENR (.3)	X
3.2.32.x	Summary of Treatment-Emergent Adverse Events by MedDRA System Organ Class, Preferred Term, and Outcome	SAF (.1), PAS (.2)	
3.2.33.x	Summary of Treatment-Emergent Adverse Events by MedDRA System Organ Class, Preferred Term, and Action Taken With Tafasitamab	SAF (.1), PAS (.2)	
3.2.34.x	Summary of Treatment-Emergent Adverse Events by MedDRA System Organ Class, Preferred Term, and Action Taken With Lenalidomide	SAF (.1), PAS (.2)	X
3.2.35.1.x	Summary of Time to Onset of Neutropenia Since Cycle 1 Day 1	SAF (.1), PAS (.2)	
3.2.35.2.x	Summary of Time to Onset of Febrile Neutropenia Since Cycle 1 Day 1	SAF (.1), PAS (.2)	
3.2.36.1.x	Summary of Time to Onset of Neutropenia Since First Dose of Tafasitamab	SAF (.1), PAS (.2)	
3.2.36.2.x	Summary of Time to Onset of Febrile Neutropenia Since First Dose of Tafasitamab	SAF (.1), PAS (.2)	
3.3.1.1	Summary of Laboratory Values - Hematology	SAF	X

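### The protocol plans the laboratory analyses on both the PAS and the SAF; the SAP plans them on the SAF only and gives no reason

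*SAP*

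**What the plan says.** **Protocol.** Section 10.3.7.2 (Clinical Laboratory Evaluation) closes with "The analyses will be performed on PAS and SAF. Further details will be specified in the SAP". The next section, 10.3.7.3 on vital signs, names the SAF alone. Section 10.3.3, headed as the primary endpoint, says that "the incidence and severity of hematological and non-hematological AEs including clinically significant laboratory abnormalities will be determined". The primary estimand is defined on "Endpoint: Incidence and severity of TEAEs".

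**SAP.** Section 10.3.3 on laboratory summaries says "Results will be presented for the SAF". Appendix A gives the SAF as the only population for every laboratory table from 3.3.1.1 to 3.3.4.4. Most TEAE and exposure tables in the same appendix carry a paired suffix, .1 for the SAF and .2 for the PAS.

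On safety analyses in general the SAP says two things. Section 5.3.5: "All safety analyses will be conducted using the SAF". Section 10.2.4.1.1: "The primary safety analysis will be performed for the PAS, and a supplemental safety analysis will be performed for the SAF".

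SAP Section 12 lists the two SAP versions with their dates and explains no change.

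**The concern.** The protocol names two analysis sets for the laboratory data and the SAP drops one without comment. The dropped set is the one built for the primary estimand: under SAP 5.3.2 the PAS requires at least one tafasitamab dose of 24 or 30 mg/kg. Under Protocol 7.1.1 the Cycle 1 doses on Days 1, 4 and 8 are 12 mg/kg, and the SAP's infusion-rate schedule for 24 and 30 mg/kg (6.4.2.4.3) begins at Cycle 1 Day 15. So the SAF can include patients who stopped before the dose under study, among them anyone who stopped early for toxicity.

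Cytopenia is where this matters most. Neutropenia, anaemia and thrombocytopenia are the three most frequent blood disorders in the protocol's own L-MIND table (Table 7). If the SAP is followed, no summary table grades blood counts by their numerical value for the higher-dose patients alone.

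**Working it through.** The plan states no figure to reproduce, and the study has no formal test. The check is a comparison of text plus a bound on the effect.

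**1. Sets named for each type of safety data**

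| Data | Protocol | SAP |
|---|---|---|
| TEAEs | PAS for the primary estimand, SAF for the supplemental one (10.2.7, 10.3.8) | PAS primary, SAF supplemental (10.2.4.1.1) |
| Laboratory values | PAS and SAF (10.3.7.2) | SAF (10.3.3, Appendix A) |
| Vital signs | SAF (10.3.7.3) | SAF (10.4.2) |

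Only the laboratory row disagrees. Because the protocol gives vital signs a different set in the very next section, its choice for laboratory data looks deliberate.

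**2. Tables affected.** Four panels (hematology, chemistry, coagulation, liver biochemistry) by four table types (values, shift to worst abnormal value, CTCAE shift, treatment-emergent worsening): 4 × 4 = 16.

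**3. What the PAS still receives.** SAP 10.2.1.1 has qualifying laboratory abnormalities entered in the eCRF as AEs. These flow into the PAS versions of the TEAE tables (for example 3.2.5.2, by CTCAE grade), into Figure 4.5.2.2 (hematologic TEAEs) and into the time-to-onset tables 3.2.35 and 3.2.36. The laboratory element that Protocol 10.3.3 places in the primary safety analysis is therefore reported on the PAS.

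**4. What the PAS does not receive.** TEAE entry depends on investigator judgement. Under Protocol Appendix 12 an abnormal result is an AE if judged clinically significant, and findings associated with the underlying disease are left out unless worse than expected. SAP 10.2.1.1 derives no further AE entries by program. Inclusion criteria 7a and 7b admit patients whose low counts come from marrow involvement, so attribution to disease is a real possibility. The shift and worsening tables grade the measured value against CTCAE whatever the attribution. That analysis is planned only on the SAF.

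**5. Size.** Let N be the number in the SAF, k the number of those outside the PAS, y the events among those k, and x the events in the PAS. Then

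(x + y)/N − x/(N − k) = (k/N) × [y/k − x/(N − k)].

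The bracket lies between −1 and 1, so the absolute difference is at most k/N. Taking N as about 51 (planned enrollment) and k as an assumption:

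| k | PAS size | Largest possible difference, k/51 |
|---|---|---|
| 0 | 51 | 0.0 points |
| 1 | 50 | 2.0 points |
| 2 | 49 | 3.9 points |
| 3 | 48 | 5.9 points |
| 5 | 46 | 9.8 points |
| 8 | 43 | 15.7 points |

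This bound is for proportions with the whole set as denominator, which can describe at most the four worsening tables (3.3.4.x). For shift tables SAP 10.3.3 uses the baseline category as denominator (3.3.2.x and 3.3.3.x, eight tables). There the same formula holds with N and k counted within the category. Tables 3.3.1.x are mainly descriptive statistics of values, to which it does not apply.

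**The case against.** A reader might infer that the laboratory part of the primary safety objective goes unreported for the primary estimand's population. The documents do not support that. The endpoint is TEAEs; laboratory findings enter it as clinically significant abnormalities within AEs, and those are tabulated on the PAS. Laboratory values sit in Protocol 10.3.7, under additional safety analysis.

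A reader might also infer that the laboratory and AE tables cannot be read together. They can be, on the SAF: the TEAE tables planned on the PAS also have SAF versions. Subject-level laboratory listings (2.8.1.x) and an analysis-population listing (2.3.1) are planned as well. Only the PAS-to-PAS comparison in summary tables is missing.

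Three further points deserve weight.

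- SAP 5.3.5 does not say the SAF is the only set, and the more specific 10.2.4.1.1 settles what is done for TEAEs. This stands in part: the conflict is one of wording, but as written 5.3.5 leaves no place for a primary analysis on the PAS.
- The protocol defers detail to the SAP, and Protocol 10.3 already requires departures from plan to be explained in the study report. Neither point answers the gap: deferring detail does not remove a named set, and a later explanation does not produce the missing summary.
- The treatment-group definition in SAP 5.2 is cut off in the public copy, so it cannot be checked whether by-group SAF columns would already separate patients who never reached 24 or 30 mg/kg. This stands as a limit on what can be said about impact.

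**Conclusion.** The point holds as a mismatch between protocol and SAP, of minor severity. Following the SAP would omit a laboratory-value analysis that the protocol specifies for the patients who received 24 or 30 mg/kg. The TEAE tables on the PAS cover part of the same ground but do not replace it, because they rest on investigator judgement rather than on the graded value. SAP 5.3.5 needs correcting in any case.

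That much rests on the text alone. The practical size rests on an unknown, the number of SAF patients outside the PAS. If there are none, the two analyses coincide; otherwise a whole-set proportion moves by no more than k/51, and the k values tabulated above are assumptions. No particular distortion can be claimed.

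**What to change.** 1. Add PAS versions of Tables 3.3.1.x to 3.3.4.x, using the .1/.2 suffix convention of the TEAE tables, and amend SAP 10.3.3 to name both sets, as Protocol 10.3.7.2 requires.
2. Reword SAP 5.3.5 so that the PAS is primary for TEAEs, the laboratory analyses use both PAS and SAF, and the SAF serves the supplemental TEAE analysis and the remaining safety analyses.

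If the PAS was left out on purpose, the departure from Protocol 10.3.7.2 and its reason should be recorded, though that alone would not supply the missing summary.

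The cost is a rerun of existing laboratory programs on a second population, sixteen additional tables, and a short text change. No new data are needed.
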